7.1. Endpoints

Complete Mayo score: The Full Mayo score in SAP v2.0.

The 9-point Mayo score: The sum of the Rectal Bleeding subscore, Stool Frequency subscore, and the Endoscopy subscore. The 9-point Mayo score has a range of 0-9 points.

OLP Efficacy Endpoints

Clinical Remission

- Four-component Mayo clinical remission: Complete Mayo score of <=2 points with no individual subscore of >1 point
- Three-component Mayo clinical remission: Rectal bleeding subscore=0 and stool frequency subscore <=1 (and a decrease of >=1 point from the baseline stool frequency subscore), and endoscopy subscore <=1

Clinical Response

- Four-component Mayo clinical response: Reduction from baseline in complete Mayo score of >=3 points and reduction from baseline in complete Mayo score of >=30%, and (reduction in rectal bleeding subscore of >=1 point or a rectal bleeding subscore of <=1 point)
- Three-component Mayo clinical response: Reduction from baseline in the 9-point Mayo score of >=2 points and Reduction from baseline in the 9-point Mayo score >=35%, and (reduction from baseline in the rectal bleeding subscore of >=1 point or a rectal bleeding subscore of <=1 point).

Mucosal Healing

- Mucosal Healing is defined as an Endoscopic subscore of ≤ 1 point
- Mucosal healing (alternative definition): Endoscopy subscore of <=1 point and a Geboes index score <2.0

Histological remission

• Histological remission is defined as Geboes index score < 2.0.

Analysis visit windows defined in Section 7.3 will be applied on all efficacy analyses.

7.2. Mayo Score at the End of OLP

The analyses will be carried out when all patients have completed (or would have been eligible to complete) the OLP of the study. The mayo score will be summarized using descriptive statistics.

The proportion of patients in clinical remission, clinical response, and with mucosal healing will be descriptively summarized at each visit window defined in Section 7.3 in the OLP ITT population.

The proportion of patients in partial Mayo clinical remission and in partial Mayo clinical response will be descriptively summarized for each OLP visit in the OLP ITT population.

The proportion of patients in clinical remission (for all bullet definitions listed in Section 7.1), in clinical response (for all bullet definitions listed in Section 7.1), and with mucosal healing will also be descriptively summarized as described above in the same subgroups as the Core period in the OLP ITT population.

- Prior anti-TNFα use (yes vs. no)
- Age (\leq median vs. \geq median)
- Sex (Female vs. Male)
- Disease localization (Left side vs. Extensive)
- Baseline disease activity (Mayo score using the central endoscopy read $\leq 8 \text{ vs.} > 8$)

The proportion of patients in clinical remission (for all definitions), in clinical response (for all definitions), and with mucosal healing will be descriptively summarized as described above in the OLP ITT population using:

- Observed cases
- NRI

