6.12. Demographics and Baseline Characteristics

The demographics and baseline characteristics will be presented in a table. The demographic characteristics consist of age, age category, sex, race, ethnicity, weight, height, body mass index (BMI), smoking history, and stratification factors. Age, weight, height, BMI, years as a smoker, and numbers of cigarettes, cigars, and pipes smoked per week will be summarized using the descriptive statistics. The number and percentage of patients in each age category (18-29, 30-39, 40-49, 50-59, 60-69, and 70-75, and < median, ≥ median) and in each race category (White, Black, Asian, American Indian or Alaska Native, Native Hawaiian or Other Pacific Islander, and Other) will be reported. The number and percentage of patients who have ever smoked, are current smokers, and who smoke each type of tobacco product will be reported. The summaries will be presented for the ITT population. Listings will be provided for demographic and baseline characteristic data.

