6.14. Ulcerative Colitis Disease History

The following UC disease history parameters will be summarized using descriptive statistics:

- Age at UC diagnosis
- Years since UC diagnosis
- Mayo score at Baseline (using the central endoscopy score)
- Mayo score subgroup proportions using the central endoscopy score ($< 8 \text{ vs.} \ge 8$)
- Mayo score at Baseline (using the investigator endoscopy score)
- Mayo component scores at Baseline (stool frequency, rectal bleeding, physician's global assessment, investigator endoscopy score, central endoscopy score)
- Extent of disease (limited to left side of colon or extensive).

For partial UC diagnosis dates, the following imputation methods will be applied:

- If month and year are present but day is missing, then the day will be set to the 15th
- If year is present but not month and day, month and day will be set to July 1st
- If either imputation above results is a date >= the date of informed consent, then impute the date as informed consent date 1.

UC disease history will also be listed.

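### The open-label addendum says it uses the core-period subgroups, but its age groups overlap at the median and its Mayo cut puts a score of 8 on the other side from SAP 6.14.

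*SAP*

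**What the plan says.** SAP OLP addendum, section 7.2, plans descriptive summaries of remission, response and mucosal healing "in the same subgroups as the Core period in the OLP ITT population". It lists five subgroups: prior anti-TNF use, age, sex, disease localization and baseline disease activity.

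- Age is given as "Age (\leq median vs. \geq median", that is, at or below the median against at or above it.
- Disease activity is given as "Baseline disease activity (Mayo score using the central endoscopy read", with the cut at ≤ 8 versus > 8.

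SAP v2.0 shows two corresponding splits, both in baseline tables.

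- Section 6.12 (demographics) ends its age categories with "and < median, ≥ median".
- Section 6.14 (disease history) lists "Mayo score subgroup proportions using the central endoscopy score", with the cut at < 8 versus ≥ 8.

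Three other statements bear on the point. SAP 5.4 reports age as an integer. Addendum section 6 derives the OLP efficacy endpoints from the core baseline. SAP 6.19.4 (Exploratory Efficacy Analyses), where core efficacy subgroups would be expected, shows only its heading in the public text, and the text of Protocol 13.8.4 is blacked out.

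**The concern.** The addendum tells its reader that the OLP subgroups are the core ones. For age and disease activity, the printed boundaries are not those of SAP 6.12 and 6.14.

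For age, the two groups are not mutually exclusive. Programmed as written, any patient at the median enters both columns, and the subgroup counts add up to more than the OLP total. For disease activity, the groups are exclusive, but the patients scoring 8 sit on the opposite side from SAP 6.14. A reader who sets a core table by disease activity beside the OLP table would take the groups to be the same when they are not.

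The definitions carry through many cells. Addendum 7.1 has two definitions each of remission and response, plus mucosal healing. Addendum 7.3 has six windows for the full Mayo score (Weeks 56, 104, 152, 200, 248 and 296), and results are shown by parent treatment group.

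**Working it through.** The plan states no count, power or rate for these subgroups, so there is no figure of its own to reproduce. The check compares the boundaries and then sizes the effect under stated assumptions.

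**Step 1: the five subgroups side by side**

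| Subgroup | Addendum 7.2 | SAP v2.0 | Agree? |
|---|---|---|---|
| Prior anti-TNF | yes / no | yes / no (stratification factor, 6.7) | yes |
| Age | ≤ median / ≥ median | < median / ≥ median (6.12) | no |
| Sex | female / male | no cut-point needed | yes |
| Localization | left side / extensive | left side / extensive (6.14) | yes |
| Baseline Mayo, central read | ≤ 8 / > 8 | < 8 / ≥ 8 (6.14) | no |

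**Step 2: who moves on the Mayo split**

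Eligible scores are the integers 6 to 12 (Protocol 9.5.1).

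| Score | 6 | 7 | 8 | 9 | 10 | 11 | 12 |
|---|---|---|---|---|---|---|---|
| SAP 6.14 | low | low | high | high | high | high | high |
| Addendum 7.2 | low | low | low | high | high | high | high |

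Only a score of 8 changes side. The documents do not give the share of patients at 8. A uniform spread over seven scores gives 1/7 = 14.3%. For an assumed range of 10–30%:

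- 100 OLP patients: 100 × 0.10 = 10 to 100 × 0.30 = 30 patients change group.
- 180 OLP patients (all randomized, the upper bound): 180 × 0.10 = 18 to 180 × 0.30 = 54 change group.

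**Step 3: how many patients sit at the median age**

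If the median is taken in the OLP population and that population is odd in number, the median is an observed age and the overlap is certain. If it is even, the overlap may be empty. The number of ties was simulated with 4,000 samples per setting. Ages were drawn from a normal distribution with mean 41, rounded down and restricted to 18–75. The mean, the SDs and the OLP sizes are all assumptions.

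| OLP size | Mean number at the median (SD 16 to SD 10) | Chance of at least one |
|---|---|---|
| 100 | 2.7 to 4.0 | 66% to 76% |
| 140 | 3.9 to 5.6 | 76% to 82% |
| 180 | 4.9 to 7.1 | 79% to 86% |

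The widest 5th-to-95th percentile range is 0 to 12.

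**Step 4: largest effect on an age-group rate**

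Let N be the OLP size, k the number at the median, h = (N − k)/2 the number on each side, and r an assumed 40% rate. Compared with < median versus ≥ median, only the lower group changes. The largest change, if all k respond, is k(1 − r)/(h + k).

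- N = 180, k = 6: h = 87; 6 × 0.6/93 = 3.9 percentage points; the subgroup counts sum to 186.
- N = 100, k = 4: h = 48; 4 × 0.6/52 = 4.6 percentage points; the subgroup counts sum to 104.

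These are pooled over parent treatment groups.

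**The case against.** The strongest reply is that the core efficacy subgroups cannot be seen. SAP 6.12 and 6.14 define categories for baseline tables, and neither says that the same cuts were used for efficacy. If SAP 6.19.4 used ≤ 8 versus > 8, the addendum is faithful to it and the mismatch lies inside SAP v2.0. Changing the addendum to < 8 versus ≥ 8 would then create the inconsistency it was meant to remove. This stands, and it is why the Mayo fix has to be conditional. It does not remove the need to reconcile: SAP 6.14 calls its split a subgroup, uses the same central read, and would still disagree with the efficacy tables.

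Second, a sign may have been misread when the PDF was turned into text. For age, one stray underline would create the overlap. The liver-test categories in SAP 6.20.6, which switch between strict and non-strict signs, suggest caution. This stands for age. For Mayo, both signs would have to be wrong in a complementary way, which is less likely.

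Third, the harm is small. The summaries are descriptive, and the visible text plans no core-to-OLP subgroup comparison. Such a comparison would be loose anyway: all OLP patients receive 1 mg, they enter by different routes, and the treatment failure rules are dropped. This stands and limits the weight of the point.

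A reader might infer that the OLP subgroup results are wrong, or that none can be set beside the core. The documents do not support that. A split at ≤ 8 versus > 8 is exclusive, exhaustive and valid for the groups it defines. The age overlap touches only patients at the median. The anti-TNF, sex and localization subgroups show no discrepancy.

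**Conclusion.** The point holds as a minor specification error. As printed, addendum 7.2 claims identity with the core subgroups, yet its age groups overlap and its Mayo boundary differs from SAP 6.14. The age overlap is a defect on its face, whatever the core text says, provided the sign is printed that way in the original. The Mayo mismatch with SAP 6.14 is certain on the text as it reads. A mismatch with the core efficacy subgroups is an inference, because their definition is not public.

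Neither the OLP size nor the distributions of age and Mayo score are given, so the size rests on assumptions: 10–30% of OLP patients on the other side of the Mayo split, and on average about 3 to 7 patients counted twice by age. The double counting would change an age-group rate by at most about 4 to 5 percentage points in the examples worked. The consequence is confined to the descriptive OLP tables by age and disease activity. No test, significance level or primary conclusion is affected.

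**What to change.** 1. Check the inequality signs in addendum 7.2 against the original document.
2. Print age as < median versus ≥ median, and state whether the median is that of the core ITT or the OLP ITT population.
3. Confirm the Mayo cut used for the core efficacy subgroups. If it is the one in SAP 6.14, print < 8 versus ≥ 8 on the central read. If the addendum's cut is intended, state it as a change and remove the claim that the subgroups are those of the core period.

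The cost is at most three inequality signs (one for age, two for Mayo), one sentence on the median, and the matching program lines. No new data are needed.

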7.3. Visit Windows

Post-OLP-Baseline visits (scheduled or unscheduled) during OLP will be mapped to an analysis visit based on the windowing algorithm below. If a visit cannot be mapped to any analysis visit, then the analysis visit will be set to missing and the data of interest will be excluded from summaries. If multiple visits containing the same data of interest can be mapped to the same analysis visit, the visit closest to the target day will be used in the analysis. In the event that two or more visits are equidistant to the target day, the later visit will be used in the analysis. If the two visits are on the same day, then the visit with the worst result will be used in the analysis.

Visit	Target Day	Analysis Visit Window for partial Mayo score	Analysis Visit Window for Complete Mayo Score, 9-point Mayo Score and Geboes Index
		(+/- 6 weeks)	(+/- 24 weeks)
Day 1OLP	1	N/A	N/A
Week 4OLP	36	(19-50)	N/A
Week 8OLP	64	(51 - 106)	N/A
Week 20OLP	148	(107 - 190)	N/A
Week 32OLP	232	(191 - 274)	N/A
Week 44OLP	316	(275 - 358)	N/A
Week 56OLP	400	(359 - 442)	(232 - 568)
Week 68OLP	484	(443 - 526)	N/A
Week 80OLP	568	(527 - 610)	N/A
Week 92OLP	652	(611 - 694)	N/A

Week 104OLP	736	(695 - 778)	(569 - 904)
Week 116OLP	820	(779 - 862)	N/A
Week 128OLP	904	(863 - 946)	N/A
Week 140OLP	988	(947 - 1030)	N/A
Week 152OLP	1072	(1031 - 1114)	(905 - 1240)
Week 164OLP	1156	(1115 - 1198)	N/A
Week 176OLP	1240	(1199 - 1282)	N/A
Week 188OLP	1324	(1283 - 1366)	N/A
Week 200OLP	1408	(1367 - 1450)	(1241 - 1576)
Week 212OLP	1492	(1451 - 1534)	N/A
Week 224OLP	1576	(1535 - 1618)	N/A
Week 236OLP	1660	(1619 - 1702)	N/A
Week 248OLP	1744	(1703 - 1786)	(1577 - 1912)
Week 260OLP	1828	(1787 - 1870)	N/A
Week 272OLP	1912	(1871 - 1954)	N/A
Week 284OLP	1996	(1955 - 2038)	N/A
Week 296OLP	2080	(2039 - 2122)	(1913 - 2248)
Week 308OLP	2164	(2123 - 2206)	N/A
Week 320OLP	2248	(2207 - 2290)	N/A

8. Safety Analyses

AEs will be recorded from the time written informed consent is signed through the 90-day safety Follow-up visit to ensure adequate collection of adverse events that could be associated with investigational drug.

Treatment-emergent adverse events include adverse events that started between the date of first dose of OLP and 90-day safety Follow-up visit after the date of last dose.

9. Guideline on Missing Date Imputation

The following missing data imputation rules will be applied to the OLP analyses.

Medication Dates:

If the start date of medication is completely missing in which the day, month, and year are all unknown or only the day is known, then the start date will not be imputed.

For the partial start date of medication,

- If the year is present and the month and day are missing or the year and day are present and the month is missing, set month and day to January 1.
- If the year and month are present and the day is missing, set day to 1st day of month.
- If the imputed start date of medication is after the non-imputed end date of medication, then the start date will be set to the end date of medication.

If the end date of medication is completely missing which the day, month, and year are all unknown or only the day is known, then the end date will not be imputed.

For the partial end date of medication,

- If the year is present and the month and day are missing or the year and day are present and the month is missing, set month and day to December 31.
- If the year and month are present and the day is missing, set day to last day of the month.

Adverse Event Dates:

If the adverse event onset date is completely missing, is set to date of first dose.

If year is missing, set it as the year of first dose.

If year is present but (month and/or day) are missing:

- If year = year of first dose, then set missing month and/or day to month and/or day of first dose
- If year < year of first dose, then set missing month and/or day to December and/or 31.
- If year > year of first dose, then set missing month and/or day to January and/or 1.

If month and year are present but day is missing:

- If year = year of first dose and if month = month of first dose, then set day of first dose
- If month < month of first dose, then set day to last day of the month
- If month > month of first dose, then set day to first day of the month
- If year < year of first dose, then set day to last day of the month
- If year > year of first dose, then set day to first day of the month

For all other cases, set to date of first dose.

SPONSOR: CELGENE INTERNATIONAL II SÀRL

Signature of Celgene International II Sarl

100

Representative

[name] Senior Director Global Clinical Trial Management

Printed Name of Celgene International II Sàrl Representative

dd mmm yyyy

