All patients who complete the IP and are responders (see [Section 13.8](#)) at Week 8 of the IP will enter the 24-week MP. Patients will continue to receive the same investigational drug in the MP as received during the IP, and individual patient treatment will remain blinded until all patients have reached Week 32. The last visit in the MP will occur at Week 32. Patients

who complete the MP will be given the option to participate in the OLP. Patients that enter the MP and experience disease relapse will have the option to enter the OLP.

Optional Open-Label Treatment Period (OLP)

Patients who complete the IP and are non-responders at Week 8 and those that complete the MP or experience disease relapse during the MP will have the option to enter the OLP. All patients in the OLP will receive daily study treatment with RPC1063 1 mg. There will be an 8-day dose escalation regimen consisting of 4 days of treatment with RPC1063 0.25 mg, followed by 3 days of treatment with RPC1063 0.5 mg, followed by RPC1063 1 mg.

Patients who have not shown clinical improvement 8 weeks after initiation of the OLP should discontinue from the study. Eligible patients will be transitioned into the Phase 3 open-label extension UC Study RPC01-3102 and will be able to immediately enter the study (without completing the 30-day or 90-day Safety Follow-up Visits). The OLP will continue for up to 6 years, or until marketing approval of RPC1063 for UC in the country of the clinical site (estimated to be in 2019), or completed transition of patients to Study RPC01-3102, or until the Sponsor discontinues the development program.

Safety Monitoring/Follow-up

Potential AEs of interest that may be a consequence of S1P₁ modulation will be closely monitored during the study. These AEs include bradycardia, heart conduction abnormalities, pulmonary toxicity, macular edema, cutaneous malignancy, serious or opportunistic infection, and hepatotoxicity. A DMC for the study will perform safety reviews periodically, approximately 4 times a year until the end of the Maintenance Period.

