- e. Patients who continue past Week 8 in the OLP will have the Additional OLP Visit assessments performed at 12-week intervals throughout the OLP. The OLP will continue for up to 6 years, or until marketing approval of RPC1063 for UC in the country of the clinical site (estimated to be in 2019), or the completed transition of patients to Study RPC01-3102, or until the Sponsor discontinues the development program.
- f. For females of childbearing potential only, serum beta human chorionic gonadotropin (hCG) at screening is required and a urine beta hCG is required at each visit. Between scheduled visits, monthly urine pregnancy tests should be performed by the patient. If a urine pregnancy test is positive, the Investigator will instruct the patient to suspend further RPC1063 dosing, if applicable, and schedule a follow-up appointment as soon as possible. A serum pregnancy test will be performed for confirmation, including after the 90-day Safety Follow-up Visit, if needed.
- g. Includes weight. The complete physical examination will include a full examination of the skin for lesions as well as a check for visual symptoms (i.e., blurred vision or decreased visual acuity).
- h. An interim physical examination will be conducted at Visit 5OLP and 30-day Safety Follow-up Visit. The interim PE will include areas with previously noted abnormalities and/or that are associated with any new complaints from the patient. The interim PE will also include a check for visual symptoms (i.e., blurred vision or decreased visual acuity).
- i. DLCO, if applicable, will be done at End of Open-Label/ET.
- j. The PK blood sample on Week 8 should be trough level, taken just prior to dose administration. The blood sample on End of Open-label Visit/ET should be taken 2-6 hours after dosing. The actual time of investigational drug administration for all visits with PK evaluation will be recorded on the dosing log. The blood sample at the 30-day and 90-day Safety Follow-up Visits can be collected at any point during the visit. An additional PK sample will be obtained for patients with any AE resulting in unblinding, discontinuation, or SAE.
- k. For patients who continue past Week 8 in the OLP, an endoscopy will be performed at Week 56OLP and a full Mayo score will be calculated at that time.
- l. At End of Open-Label or ET Visit sigmoidoscopy should be performed either on day of visit or no more than 7 days prior to the visit date.

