8. DEVIATIONS FROM PROTOCOL

The analyses of the following endpoints specified in the protocol are not performed due to collected samples have not been analyzed at the time of database lock.

- Proportion of patients with histologic Remission at Week 8 for exploratory objectives and exploratory efficacy endpoints.
- Plasma protein biomarkers (cytokines, chemokines, other inflammatory proteins) as PD endpoint.

STATISTICAL ANALYSIS PLAN - OPEN LABEL PERIOD ADDENDUM

Title: A Phase 2, multi-center, randomized, double-blind, placebo-

controlled parallel-group study to evaluate the clinical efficacy and

safety of induction therapy with RPC1063 in patients with

moderately to severely active ulcerative colitis

Protocol: RPC01-202

Sponsor: Celgene International II Sàrl (see appended signature page)

[name] [name]

[contact]

Date: October 15, 2019

Status: Addendum to Version 2.0

CONFIDENTIAL

This document is a confidential communication of Receptos. Acceptance of this document constitutes agreement by the recipient that no unpublished information contained herein shall be published or disclosed without prior written approval, except that this document may be disclosed to the appropriate Institutional Review Board(s)/Independent Ethics

Committee(s) under the condition that they keep it confidential.

TABLE OF CONTENTS

SIGNA	ATURES	2
TABLE	E OF CONTENTS	3
LIST O	OF ABBREVIATIONS	4
1.	Introduction	5
2.	Study Design	5
3.	Analysis Cohorts	5
4.	DMC	5
5.	Patient Disposition	5
6.	OLP Baseline	5
7.	Efficacy Analyses	6
7.1.	Endpoints	6
7.2.	Mayo Score at the End of OLP	6
7.3.	Visit Windows	7
8.	Safety Analyses	8
9.	Guideline on Missing Date Imputation	8

LIST OF ABBREVIATIONS

AE adverse event DEF definition

DMC data monitoring committee

IP Induction Period ITT intent-to-treat

[figure not shown]
MP Maintenance Period

NRI Non-responder imputation
OLP Open-Label Treatment Period

SAE serious adverse event SAP statistical analysis plan

UC ulcerative colitis

1. Introduction

Study Design

3. Analysis Cohorts

- Intent-to-Treat (ITT) Analysis Cohorts will be labeled by randomized treatment in the parent study for all subjects who received at least one dose of RPC1063 1mg in OLP.
- Safety Analysis Cohorts will be labeled by actually received treatment in the parent study for all subjects who received east one dose of RPC1063 1mg in OLP.

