4. DMC

2.

There were no DMC reviews planned for the OLP.

5. Patient Disposition

Patient disposition information will only include subjects who participated the OLP.

6. **OLP Baseline**

Baseline for efficacy analyses:

Core baseline: The last assessment prior to/on first dose date in Core Period.

The full set of the efficacy endpoints will be derived based on Core baseline.

Baseline for safety analyses:

The adverse events (AEs) will be summarized per Section 8.

For non-AE safety endpoints, definition of Baseline will not change (SAP v2.0 Section 5.1)

7. Efficacy Analyses

The efficacy measurements will be summarized by parent study treatment group at each OLP visit in the OLP ITT population. Non-responder imputation (NRI) will be used as the primary method for addressing missing binary outcomes. No treatment failure rule will be applied in the OLP, as per its defined in Section 6.19 (SAP v2.0).

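### OLP full Mayo, 9-point Mayo and Geboes values before Day 232 have no analysis visit, so the continuous end-of-OLP Mayo summary and the observed-case proportions omit them

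*SAP*

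**What the plan says.** **Windows.** SAP OLP addendum 7.3 has one window column for partial Mayo and another for complete Mayo, 9-point Mayo and Geboes. In the second column Day 1 and Weeks 4, 8, 20, 32 and 44 read N/A. The first window is Week 56OLP, target Day 400, Days 232 to 568. If a visit fits no window, "then the analysis visit will be set to missing and the data of interest will be excluded from summaries". If several visits fall in one window, "the visit closest to the target day will be used in the analysis". No row is labelled end of OLP or ET.

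**Scope.** Addendum 7.1: "Analysis visit windows defined in Section 7.3 will be applied on all efficacy analyses".

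**What is summarised.** Addendum 7.2 is headed as the Mayo score at the end of the OLP. Of the continuous score it says only: "The mayo score will be summarized using descriptive statistics". Remission, response and mucosal healing are summarised by window, using observed cases and NRI.

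**Missing data.** Addendum section 7: "Non-responder imputation (NRI) will be used as the primary method for addressing missing binary outcomes". The OLP ITT cohort (addendum section 3) is defined "for all subjects who received at least one dose of RPC1063 1mg in OLP". Section 7 also switches off the treatment failure rule of main SAP 6.19.

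**Data collection.** Protocol Table 2 marks endoscopy, full Mayo score and colonic biopsy at the End of Open-label/ET visit. Its footnote reads: "At End of Open-Label or ET Visit sigmoidoscopy should be performed either on day of visit", with up to 7 days before the visit also allowed. The only other scheduled OLP endoscopy is at Week 56OLP. Protocol 9.1 adds: "Patients who have not shown clinical improvement 8 weeks after initiation of the OLP should discontinue from the study".

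**The concern.** The protocol has two scheduled sources of full Mayo and histology data in the OLP: Week 56 and the End/ET visit. The addendum gives the first an analysis visit and the second none. An ET result is used only if its day happens to fall in a Week 56 or later window.

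The stopping instruction puts some ET visits near Day 64, far outside the first window. Those patients have an endoscopy and biopsy, and no OLP efficacy summary of full Mayo, 9-point Mayo or Geboes uses the result. The summary named for the end of the OLP then describes only patients scored on or after Day 232. If early leavers score worse, that summary looks better than the measured data.

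Nothing else in the plan brings these values back:

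- Main SAP 5.1 used eCRF visit labels, under which an ET visit would stand on its own. The addendum windows replace that for OLP efficacy.
- The carry-forward for continuous endpoints in main SAP 6.19 belongs to the treatment failure rule, which is off in the OLP.
- The addendum gives no imputation for the continuous score.

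**Working it through.** **1. Reproduce the windows.** The targets follow 7 × week + 8, so Week 56 gives 7 × 56 + 8 = 400. The half-width is 24 weeks = 168 days. 400 − 168 = 232 and 400 + 168 = 568, exactly as printed. The later windows follow the same rule, with each lower bound moved up one day to avoid overlap (Week 104: 736 ± 168 = 568 to 904, printed 569 to 904). Coverage is continuous from Day 232 to Day 2248. The post-baseline gap is Days 2 to 231, and 231 / 7 = 33 weeks.

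**2. Map test days to both columns.**

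| OLP day | Complete Mayo / 9-point / Geboes | Partial Mayo |
|---|---|---|
| 36 | none | Week 4 (19–50) |
| 64, 67, 94 | none | Week 8 (51–106) |
| 148 | none | Week 20 (107–190) |
| 231 | none | Week 32 (191–274) |
| 232 | Week 56 (232–568) | Week 32 (191–274) |

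An ET visit at about Week 8OLP (Day 64 ± 3) maps to no full-score window. Its partial Mayo, where available, does map.

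**3. Binary endpoints (assumed figures).** Let q be the share leaving before Day 232 with an ET endoscopy. Assume 5% of them are in remission at ET, and 50% of the rest at their mapped visit.

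- Observed cases, mapped patients only: 50% for every q.
- NRI in the OLP ITT cohort: 0.50 × (1 − q).
- Last measured score whatever the day: 0.50 × (1 − q) + 0.05 × q.

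| q | Observed cases | NRI | Last measured score |
|---|---|---|---|
| 15% | 50% | 42.5% | 43.25% |
| 25% | 50% | 37.5% | 38.75% |
| 35% | 50% | 32.5% | 34.25% |

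NRI lies 0.75 to 1.75 points below the last-score figure. Observed cases lie 6.75 to 15.75 points above it.

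**4. Continuous score (assumed figures).** Let f be the share leaving before Day 232. Assume a mean Mayo score of 3 in mapped patients and 8 in early leavers. The mean over all measured last scores is 3(1 − f) + 8f = 3 + 5f. The windowed mean stays at 3.0.

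| f | Windowed mean | Mean with early leavers |
|---|---|---|
| 10% | 3.0 | 3.5 |
| 20% | 3.0 | 4.0 |
| 30% | 3.0 | 4.5 |
| 40% | 3.0 | 5.0 |
| 50% | 3.0 | 5.5 |

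The gap is f times the difference in means. It vanishes if the two groups score alike, and reverses if early leavers score better.

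**5. Two scores in one window.** Take a Week 56 score on Day 400 and an ET score on Day 500. Both fall in Days 232 to 568, at distances 0 and 100 from the target. The Day 400 score is used and the ET score is not, although the ET score is the patient's status at the end of the OLP.

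**The case against.** The strongest reply is that this is ordinary by-visit windowing, read as if it should do something else.

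- A Day 64 endoscopy is not a Week 56 observation, and observed cases by definition rest on patients with data. NRI is shown alongside and is the primary method.
- The Week 56 start matches the protocol, which schedules no earlier OLP endoscopy for patients who continue.
- Partial Mayo is kept from Day 19, so patients without improvement do appear in the Week 8OLP summaries. Main SAP 6.1 lists all individual data.
- A patient whose later ET score is displaced, and who has no further score, counts as a non-responder at Week 104 under NRI. The tie rules lean cautious: the later visit if equidistant, the worse result if on the same day.
- The OLP is uncontrolled, uses one dose and is summarised descriptively. No confirmatory test depends on it.

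All of this stands for the by-visit tables, which need no change. It does not answer the end-of-OLP summary. Section 7.2 is headed for that time point, 7.3 has no such analysis visit, and 7.1 sends every efficacy analysis through 7.3. The continuous score has no NRI counterpart to show the reader what was left out.

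**Conclusion.** The gap is real but narrow. Complete Mayo, 9-point Mayo and Geboes values from OLP Days 2 to 231 are excluded by rule. They are therefore absent from the continuous end-of-OLP Mayo summary and from the observed-case proportions. A later ET score can also be displaced by a Week 56 score in the same window.

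Two stronger readings are tempting, and the documents support neither. A reader might infer that the addendum inflates OLP remission and response rates in general. It does not: the rule removes data, not patients, and under the primary NRI method early leavers stay in the denominator as non-responders. A patient in response at an early ET visit is even counted against the drug. A reader might also infer that everyone lost this way is a drug failure. Adverse events, withdrawal, non-compliance and transfer to Study RPC01-3102 can also end OLP participation early.

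The documents do not give the share leaving before Day 232 or their scores, so the size of any bias is unknown. The figures in the working are illustrations. The direction is probably favourable to the drug, on the assumption that early leavers score worse on average. Only descriptive, uncontrolled results are affected, so this should be corrected but does not threaten the trial's main conclusions.

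**What to change.** Add to addendum 7.3 an analysis visit, End of OLP/ET, holding each patient's last complete Mayo, 9-point Mayo and Geboes value in the OLP whatever the day. In 7.2, state that the end-of-OLP summary uses this visit, for the continuous score and for the observed-case proportions. Report beside it the number of patients whose last score came before Day 232. Keep the Week 56 and later windows, and the closest-to-target rule, unchanged for the by-visit tables.

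The cost is about two sentences and one more table column, with no new data. One small drawback is that the last-score column mixes different lengths of exposure, so it should be labelled that way.
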